## JTA- KOA1 - Clinical Study Protocol

JTA-KOA1-CSP	V 04	Author: EB	Date: May 10, 2017	Pg. 5/114
--------------	------	------------	--------------------	-----------

## STUDY SYNOPSIS

EudraCT Number: 2015-002117-30 Protocol Number: 000010/BT Protocol Code: JTA-KOA1	Test product: JTA-004 Reference: Synvisc-One®
Sponsor: Bone Therapeutics S.A., [name]	
Title: A two-stage 6-month, Multicentre, Randomised, Double-blind, Controlled Study on the Safety and Efficacy of Single Intra-articular Administration of JTA-004 in Patients with Symptomatic Knee Osteoarthritis	
Phase of Development: Two-stage Phase II/Phase III trial	
Number of Centres / Countries: up to 15 centres in Belgium	
Planned Study Period: Total recruitment period: until 164 patients have been included (this number may be adjusted upon sample size reassessment at interim analysis). Total study follow-up period: 6 months	
Study design: This study is a seamless two-stage prospective, randomized, double-blind controlled Phase II/Phase III trial including 3 JTA-004 strengths with 1 reference product. The initial phase of the two-stage design plans for selection of the best JTA-004 strengths for a confirmatory phase testing for superiority compared to a best in class reference treatment.	
Planned Number of Patients: A total of 164 patients are planned.	
Medical Condition under Investigation: symptomatic osteoarthritis of the knee with Kellgren-Lawrence grade II and III.	

## JTA- KOA1 - Clinical Study Protocol

JTA-KOA1-CSP

V 04

Author: EB

Date: May 10, 2017

Pg. 6/114

**Inclusion Criteria:**

- Male/female aged between 50 to 79 years
- Diagnosed with primary knee OA, fulfilling the following American College of Rheumatology (ACR) criteria at the target knee:
  - Pain  $\geq$  40 mm on a 0-100 mm VAS during the 3 days preceding the date of the Screening Visit (see Annex 2)
  - Morning stiffness not exceeding 30 minutes
  - Kellgren-Lawrence grade II or III (confirmed by X-ray within the last 6 months)
- Insufficient/failed response to analgesic and/or NSAID

**Main Exclusion Criteria**

- Concomitant inflammatory disease or other condition affecting the joints (e.g., rheumatoid arthritis, septic arthritis, metabolic bone disease, psoriasis, gout, microcrystalline arthropathies/chondrocalcinosis, Paget's disease...)
- Treatment:
  - Within 6 months prior to Screening: intra-articular hyaluronic acid injections into the target knee
  - Within 2 months prior to Screening: intra-articular glucocorticoids at the target knee
- Current or past history of coagulation disorders, as judged by the Investigator
- Hypersensitivity to any components of HA-based injection products
- Hypersensitivity to human biological material including blood and blood derived products, potential excipients and residues from manufacturing process, documented clinically or by laboratory tests
- Hypersensitivity to avian proteins
- Current anti-hypertensive medication known to be potentiated by a single dose of clonidine

**JTA- KOA1 - Clinical Study Protocol**

JTA-KOA1-CSP

V 04

Author: EB

Date: May 10, 2017

Pg. 7/114

**Test Product Strength and Mode of Administration:**

*Test Product:* 3 different strengths of JTA-004 (JTA-004 50 (2ml), JTA-004 100 (2ml) and JTA-004 50 (4ml) and one reference will be tested. All patients will be treated by a single intra-articular administration at visit #2.

**Study Visits:** There will be 5 visits defined as follows:

- Screening visit (Visit #1)
- Baseline/Treatment visit (Visit #2)
- Follow-up visits at 2 weeks (Visit #3), 3 months (visit #4) and 6 months (visit #5)

**Study Endpoints and Criteria for Evaluation:**

The WOMAC® VA 3.1 pain subscale scoring at baseline and subsequent assessment time points is the major efficacy criteria

Safety Endpoints

At each follow-up visit, patients will be assessed for the occurrence of any (serious) adverse events using patient open non-directive questionnaire, physical examination (including vital signs), and laboratory measurements. The safety analyses will be based on incidence evaluation of treatment emergent adverse events by preferred term and body system. Laboratory measurements will be compared to the normal laboratory ranges and to laboratory measurements obtained at Baseline Visit.

The final Study Report will be established at Month 6.

Evaluation Time Points

Safety and efficacy endpoints will be evaluated at each of the 3 follow-up visits during the 6-month follow-up period (notably at 2 weeks, 3 months and 6 months after study drug administration).

**Statistical Analysis:** Full Analysis Set (FAS) will be used for the selection of the most effective strength and for the superiority objective.

**JTA- KOA1 - Clinical Study Protocol**

JTA-KOA1-CSP

V 04

Author: EB

Date: May 10, 2017

Pg. 8/114

*Primary Endpoint*

The primary endpoint is the change between baseline and Month 6 of the Western Ontario and McMaster Universities (WOMAC® VA3.1 pain subscale (subscale A).

Primary study objectives are (i) the selection of the best JTA-004 strength and (ii) superiority assessment of the best JTA-004 strength efficacy to the reference or (iii) stop the trial at interim analysis for futility. They will be determined as follow:

- For selection of best JTA-004 strength, by comparing the different JTA-004 strengths to the reference with respect to the WOMAC® VA3.1 pain subscale score (mean differences between baseline and Month 3)
- For superiority assessment, by comparing the best JTA-004 strength and reference on the mean differences in WOMAC® VA3.1 pain subscale score between baseline and Month 6, assuming a mean between group difference of 7 mm in favor of the best JTA-004 strength (i.e., difference JTA-004 minus Reference of -7 mm) with a standard deviation of 10 mm.

The following hypothesis is stated to show superiority of JTA-004 to Reference:

- H0: The difference in the mean change from baseline at Month 6 between JTA-004 and Reference is superior or equal to 0.
- H1: The difference in the mean change from baseline at Month 6 between JTA-004 and Reference is inferior to 0.

The secondary efficacy endpoints are:

- WOMAC® VA3.1 pain subscale (WOMAC® subscale A) at Month 3
- WOMAC® VA3.1 total score over the time

*Safety Analysis*

All safety analyses will be conducted on the safety population and tabulated by treatment group.

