### 10.9 Sample Size Estimation

The sample size calculation for the superiority trial for the primary endpoint – change in WOMAC® VA3.1 pain subscale from baseline to Month 6 - is based the following assumptions:

- The mean pain difference of patients treated with the JTA-004 and those treated with the reference treatment is assumed to be -7 mm (i.e. the mean JTA-004 treatment is 7 mm better than the reference). The absolute mean difference is set to 7 mm which is below the accepted MCID of the WOMAC® VA3.1 pain subscale, which is 10 mm (Ehrich *et al.*, 2000; Bellamy *et al.*, 2001);
- The standard deviation of the mean pain difference between the two treatments, estimated from the Borrás-Verdera *et al.*, 2012 and Pavelka and Uebelhart., 2011 data, are in the range of 4.7 to 6.6 mm for sample sizes between 48 and 24, respectively. To ensure maximal power, a standard deviation value of 10.5 was used for sample size estimation.);

Under the scenario of a mean between group difference of -7 mm (i.e., JTA-004 is better than control by a mean of 7 mm) with a standard deviation of 10.5 mm, thirty-seven (37) patients per group are required for analysis, reaching a power of 80% to test for superiority, keeping the type I error at 0.05 (two-sided). This would allow collecting enough efficacy data per group while avoiding exposing too many patients.

The level of drop-out is estimated to 10%. Thus 41 patients per group have to be included.

As recruitment will continue in all 4 treatment groups until the final analysis, the maximum total number of included patients will be 164 (4 x 41).

JTA-KOA1 - Clinical Study Protocol

JTA-KOA1-CSP	V 04	Author: EB	Date: May 10, 2017	Pg. 84/114
--------------	------	------------	--------------------	------------

[REDACTED]

[REDACTED]

[REDACTED]

[REDACTED]

[REDACTED]

[REDACTED]

[REDACTED]

[REDACTED]

[REDACTED]

[REDACTED]

[REDACTED]

[REDACTED]

[REDACTED]

[REDACTED]

[REDACTED]

[REDACTED]

[REDACTED]

[REDACTED]

[REDACTED]

[REDACTED]

[REDACTED]

[REDACTED]

[REDACTED]

[REDACTED]

[REDACTED]

[REDACTED]

[REDACTED]

[REDACTED]

[REDACTED]

[REDACTED]

JTA-KOA1 - Clinical Study Protocol

JTA-KOA1-CSP	V 04	Author: EB	Date: May 10, 2017	Pg. 85/114
--------------	------	------------	--------------------	------------

[REDACTED]

[REDACTED]

[REDACTED]

[REDACTED]

[REDACTED]

[REDACTED]

[REDACTED]

[REDACTED]

[REDACTED]

[REDACTED]

[REDACTED]

[REDACTED]

[REDACTED]

[REDACTED]

[REDACTED]

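### The synopsis plans on an SD of 10 mm and section 10.9 on 10.5 mm; only 10.5 gives 37 per group, and the basis stated for it needs checking as a patient-level SD

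*Combined protocol and SAP*

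**What the plan says.** The synopsis, under Primary Endpoint, sets out the superiority comparison "assuming a mean between group difference of 7 mm in favor of the best JTA-004 strength", "with a standard deviation of 10 mm". The visible synopsis gives no alpha, power or number per group. Its only size is the total of 164.

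Section 10.9 takes the same difference, which "is assumed to be -7 mm", but says that "a standard deviation value of 10.5 was used for sample size estimation". It concludes that "with a standard deviation of 10.5 mm, thirty-seven (37) patients per group are required for analysis", "reaching a power of 80% to test for superiority", with a two-sided type I error of 0.05. A 10% drop-out allowance raises 37 to 41 per group, and four groups make 164.

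To support the SD, section 10.9 cites two published studies. It describes the quantity taken from them as the SD of the mean difference between treatments, running from 4.7 to 6.6 mm for sample sizes of 48 and 24 in that order. The value of 10.5 mm is then presented as a margin above that range.

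On the total, section 10.9 says "the maximum total number of included patients will be 164". The synopsis, under Planned Study Period, says of 164 that "this number may be adjusted upon sample size reassessment at interim analysis". Section 3.1 also provides for re-estimation, at an interim analysis of 116 patients.

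**The concern.** The SD of the change score is one of the inputs that fix the trial's size, and the protocol gives two values for it. At least one is wrong as written, and a reader cannot tell from the synopsis which one was meant.

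The second issue has more at stake. A sample size for comparing two means needs the SD between patients. The figures offered in support of 10.5 mm are worded as the SD of a mean difference, and they get smaller as the sample gets larger. A patient-level SD has no reason to do that, but a standard error does. If standard errors were read as SDs, 10.5 mm would not be a cautious choice, and the stated 80% power would be well above the true figure.

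**Working it through.** **Inputs.** Difference 7 mm (synopsis and section 10.9). SD 10 mm (synopsis) or 10.5 mm (section 10.9). Two-sided alpha 0.05, power 80%, 37 evaluable per group and 10% drop-out (all section 10.9). The synopsis states no alpha or power, so those of section 10.9 are used for both SDs.

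**Method.** Two-sample t-test with n per group. Power comes from the noncentral t distribution with 2n − 2 degrees of freedom and noncentrality 7 / (SD × √(2/n)). As a rough guide, n ≈ 2 × (SD × (1.960 + 0.842) / 7)², to which the t-test adds about one patient per group.

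**1. The plan's own figure, SD 10.5 mm.**
- Rough guide: 2 × (10.5 × 2.802 / 7)² = 35.3.
- t-test: n = 36 gives 79.7% power and n = 37 gives 80.8%, so 37 are needed, as stated.
- Drop-out: 37 × 1.1 = 40.7, rounded up to 41; 4 × 41 = 164, as stated. Dividing by 0.9 instead gives 41.1, or 42 per group, which is a trivial difference.

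**2. The synopsis SD, 10 mm.**
- Rough guide: 2 × (10 × 2.802 / 7)² = 32.0.
- t-test: n = 33 gives 79.97% and n = 34 gives 81.2%, so 34 are needed.
- Drop-out: 34 × 1.1 = 37.4, rounded up to 38; 4 × 38 = 152, which is 12 fewer than 164.
- Power with 37 per group: 84.4%.

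**3. The figures cited in support of 10.5 mm.** A standard error scales as 1/√n. Between n = 24 and n = 48 it should change by a factor of √(48/24) = 1.414. The quoted figures change by 6.6 / 4.7 = 1.404.

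If they are standard errors of a difference between two equal groups, the patient-level SD follows. The document does not say whether n is per arm or the total, so both are shown.

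| Reading of n | Formula | From 4.7 mm, n = 48 | From 6.6 mm, n = 24 |
|---|---|---|---|
| Per arm | SD = SE × √(n/2) | 4.7 × √24 = 23.0 | 6.6 × √12 = 22.9 |
| Total of two arms | SD = SE × √(n/4) | 4.7 × √12 = 16.3 | 6.6 × √6 = 16.2 |

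Under either reading, the two figures lead back to nearly the same SD.

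**4. What those SDs would mean at 37 per arm for a 7 mm difference.**
- SD about 23 mm: power about 25%; about 171 per arm needed for 80%.
- SD about 16.3 mm: power about 45%; about 87 per arm needed for 80%.

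**The case against.** The operative calculation is in section 10.9. It states its inputs, and its result reproduces. The synopsis SD does not drive any number in the plan, and if it were true the trial would have more power than claimed. The synopsis is still labelled Version 03 under page headers that say V 04, so it may simply not have been updated, although that is inference. This stands, and it makes the 10 versus 10.5 mismatch a minor correction. A reader might infer that the synopsis reports a wrong power or a wrong size. It does not: it states no power, and its 164 is the same total as in sections 3.1 and 10.9.

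The standard-error reading rests on one phrase and two numbers. The cited studies cannot be consulted here, and the required size differs about two-fold according to what n means. The planning SD is 10.5 mm, not the quoted range. All of this stands as a limit on certainty. It does not remove the reason to check, because that range is the only support section 10.9 gives for 10.5 mm.

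A reader might also infer that the synopsis and section 10.9 give opposite instructions about 164. The documents do not show that. Section 10.9 explains the maximum by recruitment continuing in all four groups, so it can mean the total with no arm dropped. An adjustment could also be downward only. The two statements conflict only if an increase above 164 is allowed, and no visible text says so. The pages following the sample size text are blacked out or absent, and may already contain the re-estimation rule and any cap.

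**Conclusion.** The SD mismatch is established. Section 10.9's 37 per group follows from 10.5 mm (80.8% power) and not from 10 mm (34 per group, or 84.4% power at 37). Taken alone it is small and errs on the safe side. This comparison assumes that section 10.9's alpha and power also apply to the synopsis statement.

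The doubt about the basis for 10.5 mm is conditional. If the 4.7 to 6.6 mm are standard errors, the patient-level SD is about 16 to 23 mm, and power at 37 per arm is about 45% (n as total) or 25% (n per arm). The scaling makes this plausible without proving it. It would be wrong to conclude from these documents that the trial is underpowered. What they support is that the planning SD has not been shown to be a patient-level SD of change.

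The status of 164 is a secondary clarification.

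**What to change.** 1. Go back to the two cited studies and confirm whether 4.7 to 6.6 mm are patient-level SDs of change or standard errors of a difference, and whether 48 and 24 are per arm or totals.
2. State one verified patient-level SD of change in both the synopsis and section 10.9, and correct the wording that describes it as the SD of a mean difference.
3. Restate the power at 37 evaluable patients per arm for that SD.
4. Say in the visible wording of section 10.9 and the synopsis whether 164 is a cap or can be exceeded after the interim re-estimation. If the redacted interim text already settles this, make the two statements match it.

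The cost is a check of two sources and a few lines of protocol text. The correction itself requires no extra patients. The restated power may be less favourable than 80%.

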**JTA- KOA1 - Clinical Study Protocol**

JTA-KOA1-CSP

V 04

Author: EB

Date: May 10, 2017

Pg. 9/114

**Ethical considerations:**

This study will be conducted in accordance with applicable laws and regulations including, but not limited to, the International Conference on Harmonisation (ICH) Guideline for Good Clinical Practice (GCP) and the ethical principles that have their origins in the Declaration of Helsinki. The Institutional Review Board (IRB)/Independent Ethics Committee (IEC) must review and approve the protocol and Informed Consent Form (ICF) before any patients are enrolled. Before any protocol-required procedures are performed, the patient must sign and date the IRB/IEC-approved ICF.

**Date and Version of the Study Protocol:** September 23th, 2016 – Version 03

## JTA- KOA1 - Clinical Study Protocol

JTA-KOA1-CSP	V 04	Author: EB	Date: May 10, 2017	Pg. 10/114
--------------	------	------------	--------------------	------------

**JTA- KOA1 - Clinical Study Protocol**

JTA-KOA1-CSP	V 04	Author: EB	Date: May 10, 2017	Pg. 16/114
--------------	------	------------	--------------------	------------

**JTA- KOA1 - Clinical Study Protocol**

JTA-KOA1-CSP	V 04	Author: EB	Date: May 10, 2017	Pg. 17/114
--------------	------	------------	--------------------	------------

**LIST OF ABBREVIATIONS**

ACR	American College of Rheumatology
AE	Adverse Event
BMI	Body Mass Index
bpm	Beats per minute
CE	Conformité Européenne
COMP	Cartilage Oligomeric Matrix Protein
eCRF	electronic Case Report Form
DCF	Data Clarification Form
DMP	Data Management Plan
EC(s)	Ethics Committee(s)
FAS	Full Analysis Set
G	Gauge
GCP	Good Clinical Practice
GMP	Good Manufacturing Practice
HA	Hyaluronic Acid
HCl	Hydrochloride
IA	Intra-articular
IB	Investigator's Brochure
ICF	Informed Consent Form
ISF	Investigator Site File
IUD	Intrauterine device
IWRS	Interactive Web Response System
LOCF	Last Observation Carried Forward
MCID	Minimal Clinically Important Difference
MedDRA	Medical Dictionary for Regulatory Activities
MW	Molecular weight
NSAIDs	Nonsteroidal Anti-Inflammatory Drugs

**JTA- KOA1 - Clinical Study Protocol**

JTA-KOA1-CSP	V 04	Author: EB	Date: May 10, 2017	Pg. 18/114
--------------	------	------------	--------------------	------------

OA	Osteoarthritis
PP	Per Protocol
SA	Safety Analysis
SAE	Serious Adverse Event
SAF	Safety Set
SAP	Statistical Analysis Plan
SAR	Serious Adverse Reaction
SD	Standard Deviation
SDV	Source Data Verification
SPM	Study Procedure Manual
SSO	Study Safety Officer
SOPs	Standard Operating Procedures
TMF	Trial Master File
VAS	Visual Analogue Scale
WHO	World Health Organisation
WOCF	Worst Observation Carried Forward
WOMAC®	Western Ontario McMaster University Score

## JTA- KOA1 - Clinical Study Protocol

JTA-KOA1-CSP

V 04

Author: EB

Date: May 10, 2017

Pg. 19/114

**DEFINITIONS OF TERMS**

- **Case Report Form (eCRF):** a printed, optical or electronic document designed to record all of the protocol-required information to be reported to the Sponsor on each trial subject
- **Completed Patient:** a patient who completed all scheduled visits up to last scheduled visit (inclusive)
- **Contract Research Organisation (Monitor):** a person or an organisation contracted by the Sponsor to perform one or more of the Sponsor's trial-related duties and functions
- **Coordinating Investigator:** Investigator who is appointed by the Sponsor to coordinate work in a multicentre clinical study
- **Discontinued or withdrawn patient:** a patient who has been enrolled, screened, randomised, or treated but has withdrawn from the study before completion of the last scheduled visit
- **Double-blinding:** double-blinding is a procedure in which the patient, the Investigator, the monitor, and data analyst are kept unaware of the treatment assignments
- **Data Safety Monitoring Board (DSMB):** An independent data monitoring committee established by the Sponsor to assess at intervals the progress of a clinical trial, the safety data, and the critical efficacy endpoints, and to recommend to the Sponsor whether to continue, modify or stop the trial
- **Endpoint(s):** indicator(s) used for assessing the primary hypothesis of a study
- **Eligible patient:** screened patient (having signed and dated the informed consent form) who is considered eligible according to selection criteria
- **Enrolled patient:** patient who has dated and signed the Informed Consent Form
- **Ethics Committee (EC):** A review panel that is responsible for ensuring the protection of the rights, safety, and well-being of human subjects involved in a clinical trial and is adequately constituted to provide assurance of that protection
- **Good Clinical Practice (GCP):** set of internationally recognized ethical and scientific requirements and standards as regards to the design, conduct, performance, monitoring, auditing, recording, analyses, and reporting of clinical trials, that provides assurance that

## JTA- KOA1 - Clinical Study Protocol

JTA-KOA1-CSP

V 04

Author: EB

Date: May 10, 2017

Pg. 20/114

the data and reported results are credible and accurate, and that the rights, safety, well-being, and confidentiality of trial patients are protected

- **Informed consent:** process by which a patient voluntarily confirms his/her willingness to participate in a particular trial, after having been informed of all aspects of the trial that are relevant to the patient's decision to participate. Informed consent is documented by means of a written, signed and dated informed consent form
- **Investigation Site:** any public or private entity or hospital facility where clinical trial and trial-related activities are conducted
- **Investigational Medicinal Product (IMP):** a pharmaceutical form of an active substance or Placebo being tested or used as a reference in a clinical trial
- **Investigator:** a person responsible for the conduct of the clinical trial at a trial site. If a trial is conducted by a team of individuals at a trial site, the Investigator is the responsible leader of the team and may be called the principal investigator.
- **Investigator's Brochure (IB):** compilation of the clinical and non-clinical data on the investigational medicinal product which are relevant to the study of the product in human subjects
- **JTA-004:** reconstituted JTA-004 finished product to be administered (2 ml or 4 ml) to osteoarthritic patients and combining high molecular weight hyaluronic acid and two active medicinal substances
- **Legally authorized representative:** individual or judicial or other body authorized under applicable law to consent, on behalf of a prospective patient, to the patient's participation in the clinical trial
- **Monitor:** While ICH GCP uses the term "Monitor" instead of Clinical Research Associate (CRA), the two terms are considered to be synonymous. A Monitor is a person employed by a Sponsor, or by a Contract Research Organization (Monitor) acting on a Sponsor's behalf, who monitors the progress of a clinical trial and ensures that is conducted, recorded, and reported in accordance with the protocol, written procedures, and the applicable regulatory requirements.

## JTA- KOA1 - Clinical Study Protocol

JTA-KOA1-CSP	V 04	Author: EB	Date: May 10, 2017	Pg. 21/114
--------------	------	------------	--------------------	------------

- **Patient:** an individual who participates in a clinical trial, either as a recipient of the investigational medicinal product or a member of the reference group
- **Randomisation:** process of assigning patients to the investigational medicinal product or reference groups using an established recognized statistical methodology to determine the assignment in order to reduce bias
- **Reference (treatment):** an investigational or marketed product (e.g., active control), placebo, used in the reference in a clinical trial
- **Screened patient:** patient who has dated and signed the informed consent form (enrolled patient) and who has performed the checking of the selection criteria
- **Screening failure:** screened patient but who is not eligible for the study after checking the selection criteria
- **Serious Adverse Event (SAE):** any untoward medical occurrence or effect in a patient or clinical trial patient administered a medicinal product, which does not necessarily have a causal relationship with this treatment, and that, at any dose, results in death, is life-threatening, requires patient hospitalization or prolongation of existing hospitalization, results in persistent or significant disability or incapacity, or is a congenital anomaly or birth defect.
- **Serious Adverse Reaction (SAR):** any untoward and unintended responses to an investigational medicinal product related to any dose administered (having a reasonable causal relationship to the product), and that results in death, is life-threatening, requires patient hospitalization or prolongation of existing hospitalization, results in persistent or significant disability or incapacity, or is a congenital anomaly or birth defect.
- **Source data:** all information in original records, certified copies of original records of clinical findings, observations, or other activities in a clinical trial, necessary for the reconstruction and evaluation of the trial
- **Source document:** printed, optical or electronic document containing source data
- **Sponsor:** individual, company, institution or organization which takes responsibility for the initiation, management and/or financing of a clinical trial

